# 6. Schedule of Assessment

# **6.1.** Schedule of Assessments: Heregulin Positive Patients

Procedure Screening Visit		Cycle 1 				Cycle 2 				Additional Cycles 				Every 8 weeks	30 Day	Every 2 months
	Wk 1	Wk 2	Wk 3	Wk 4	Wk 1	Wk 2	Wk 3	Wk 4	Wk 1	Wk 2	Wk 3	Wk 4	from first dose 	Follow -Up 	from FU Visit	
Informed Consent	X															
HRG Testing	$X^1$															
Tumor Biopsy 	X															
Medical history	$X^1$															
Demographics	X 															
Vital signs	$X^2$	X		X		X		X		X		X			X	
ECOG PS	$X^2$	X				X				X					X	
CBC	$X^2$	X		X		X		X		X		X			X	
Serum chemistry	$X^2$	X		X		X		X		X		X			X	
Coagulation profile	$X^2$	X				X				X					X	
Pregnancy test	$X^2$														X	
ECG	X 	$X^{16}$				$X^{16}$				$X^{16}$						
ECHO/MUGA 	$X^1$													X	$X^{20}$	
Archived tumor, if available	X															
Fresh tumor biopsy	$X^{11}$															
Serum for seribantumab PK 		$X^{7a}$		$X^{7b}$		$X^{7b}$		$X^{7b}$								
Serum for Ig 		X				X				X					X	
Serum for biomarkers 		X				X				X						
Plasma for ESR1 testing		$X^{21}$													X	
Plasma for fulvestrant PK		$X^{12}$		$X^{12}$		$X^{12}$		$X^{12}$								
Concomitant meds	$X^1$	X		X		X		X		X		X			X	
Seribantumab dosing		X		X		X		X		X		X				
Fulvestrant dosing		X		X		X				X						
SAE/AE assessment and reporting 							•	Continuo	us monito	oring						
Hospitalization reporting 		X		X		X		X		X		X			X	X
Disease evaluation 	$X^1$													X 	X	
Overall Survival Reporting																$X^{15}$

Proprietary and Confidential Page 43 of 65

-  Procedures to be completed within 28 days of signing the **main** informed consent form
-  Procedures to be completed within 7 days of first dose of Seribantumab
-  Two independent readings at least 5 minutes apart
-  Evaluations may be performed  $\pm$  1 week from the scheduled date of visit
-  Any patient that comes off treatment for reasons other than progressive disease, will have a scan to assess disease status at the time of treatment discontinuation and additional scans every 8 weeks (+/- 1 week) until investigator-assessed PD
-  All procedures should occur ±2 calendar days from scheduled date of visit

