# 6.3. Screening and Baseline Visit

All procedures for screening and baseline are outlined in Section 6.1. The window for screening procedures begins after signing the main consent form. For further descriptions of the clinical and laboratory assessments required, please refer to Section 7 and 8 respectively.

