## **3. ENDPOINTS**

## 3.1 Progression-Free Survival – Investigator Assessed

Investigator Assessed (IA) tumors assessments are those determined by the investigator. PFS is defined as the number of months from the date of randomization to the date of death or documented (objective) disease progression via RECISTv1.1, whichever occurs earliest. Length of PFS will be calculated in days and reported in months.

[Progression/Death/Censor Date - Randomization Date + 1] / 30.4375.

The tumor assessment (i.e., scan dates) will be used for progression/censor date not the date corresponding to the determination of overall response. When multiple dates occur for assessing target, non-target, and new lesions the following rule will be applied:

- If documented disease progressions, the *first* available date will define the tumor assessment date
- If censored, the *last* available date will define the tumor assessment date.

Per protocol tumor assessments are scheduled to be performed every 8 weeks ( $\pm$  7 days) from day of first dose until investigator-assessed progression, in addition to a 30-day follow-up.

**Censorship**: In general, patients are censored at the date of the last tumor assessment that verified lack of disease progression if they are last known to be alive, on-treatment or within 30 days following treatment discontinuation, and progression-free. Censoring is explicitly described below and in table 1. Patients that do not experience progression or death by the time of analysis (data cut-off) will be censored at the date of last tumor assessment defined by any overall response other than "not evaluable".

- Patients with an inadequate/incomplete baseline tumor assessment will be censored at the date of randomization
- Patients with no tumor assessment after dosing will be censored at the date of randomization unless death occurred prior to the first planned assessment (in which case the death is an event)
- Patients with at least one on-study disease assessment who discontinue treatment without documented disease progression or death are censored at the date of the last tumor assessment

There are two exceptions.

- $\circ$  Documented progression or death  $\leq$  30 days after treatment discontinuation then progression or death is an event

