#### Table 3.1 Documented Disease Progression and Censoring

Situation	Date of	Outcome
Inadequate baseline tumor assessment No on-treatment assessment and no death prior to first scheduled assessment	Randomization	Censored
Death or documented disease progression after ≥ 2 consecutively missed and/or not evaluable scheduled tumor assessments	Last tumor assessment documenting no disease progression	Censored
Alive, on-treatment, and no documented disease progression	Last tumor assessment documenting no disease progression	
Documented disease progression (on, prior to, or $\leq 30$ days after treatment discontinuation)	First tumor assessment documenting disease progression	Progression (Event)
New anticancer treatment $\leq$ 30 days after treatment discontinuation without disease progression	Last tumor assessment documenting no disease progression prior to starting the new anticancer treatment	Censored
Treatment discontinuation due to toxicity, undocumented disease progression, or any other reason	Last tumor assessment documenting no disease progression prior to discontinuation	Censored
Death prior to first scheduled assessment	Death	Death (Event)
Death without documented disease progression and $\leq 30$ days after treatment discontinuation	Death	Death (Event)

Note: Follow-up scans can be performed up to 4 weeks from last treatment dose date via protocol

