#### 3.8 Covariates

Baseline evaluations are those collected within 28 days prior to the start of treatment. If more than one baseline evaluation is available, select the closest non-missing value prior to first dose. The closest non-missing observation may be selected on the day of cycle 1 day 1 if study procedures are indicated prior to dosing.

The following baseline characteristics will be included as covariates which may be included in model testing exercises: Age, gender, race, ethnicity, primary diagnosis and time from primary cancer diagnosis to randomization, time since last prior systemic treatment, investigative site, and others may be identified.

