## 4.2 Tumor Assessments

Inadequate tumor assessment does not allow for a RECIST response determination and will be designated as Not Evaluable target response evaluation. An inadequate assessment will be defined as those with at least 1 missing measurement or non-measurable target lesion or baseline tumor assessments outside the screening evaluation window (i.e., after first dose date and prior to -28 days from first dose date). If a target lesion is too small to measure and does not have unequivocal complete disappearance, a default of 5mm will be assigned.

Different imaging of lesions should not be performed. Those tumor assessments that do not vary based on different imaging will be allowed. However, imaging variations that result in PR or CR based on the inconsistency of imaging will be reviewed carefully and may result in confirmation of that result at the following visit.

If non-target disease is not assessed and a patient is considered for a CR target response the overall disease response will be PR.

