## **RECORDING TUMOR ASSESSMENTS**

All sites of disease must be assessed at baseline. Baseline assessments should be done as close as possible prior to study start. For an adequate baseline assessment, all required scans must be done within 28 days prior to treatment and all disease must be documented appropriately. If baseline assessment is inadequate, subsequent statuses generally should be not evaluable.

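### If this SAP is applied to the trial, its baseline-scan window (28 days before first dose) conflicts with the protocol's (28 days from main consent), and a compliant patient can be censored at randomisation in the primary PFS

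*SAP*

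**What the plan says.** **SAP, window.** Section 4.2 counts among inadequate assessments "baseline tumor assessments outside the screening evaluation window (i.e., after first dose date and prior to -28 days from first dose date". Read literally, no date is both after first dose and earlier than day -28, but the appendix on recording tumor assessments makes the intent plain: "all required scans must be done within 28 days prior to treatment". Section 3.8 uses the same first-dose anchor for baseline covariates.

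**SAP, consequence.** Section 3.1: "Patients with an inadequate/incomplete baseline tumor assessment will be censored at the date of randomization". Table 3.1 repeats this under "Inadequate baseline tumor assessment", with the date set to randomisation and the outcome to censored.

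**Protocol, window.** In the schedule in 6.1, the screening disease evaluation carries footnote 1: "Procedures to be completed within 28 days of signing the" main informed consent form. Section 6.3 adds: "The window for screening procedures begins after signing the main consent form". Footnote 2 of the same schedule ties other procedures, such as blood counts, to first dose, so the protocol keeps the two anchors apart. Section 3.1 allows up to 7 days from randomisation to first dose.

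**Protocol, consequence.** The synopsis also censors at randomisation when there is no valid tumor evaluation at that point, but it does not say what makes one valid. Section 10.5.1 leaves the details of censoring to the SAP.

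**Applicability.** SAP sections 1 and 1.2 name protocol 02-03-10 and a phase 3 design with exemestane or fulvestrant. The present protocol is 02-02-10, a phase 2 trial with fulvestrant.

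**The concern.** The SAP presents its limit as the screening window, yet measures it from a different date than the protocol does. A site can follow the protocol exactly and still produce a baseline scan that the SAP rejects. Since the protocol leaves *valid* undefined and hands censoring to the SAP, the SAP definition would decide who counts.

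The consequence falls on the primary endpoint. A patient censored at randomisation contributes no follow-up, so a later documented progression, or a later death, is discarded. The patient was eligible, was randomised and had an evaluable scan before dosing. Censoring at randomisation when there is truly no usable baseline is not disputed; the definition that triggers it is.

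**Working it through.** **1. Can a compliant scan fail the SAP window?** Let S be days from main consent to scan (0 to 28, protocol 6.1 and 6.3), R days from main consent to randomisation (no cap in the supplied text), and D days from randomisation to first dose (0 to 7, protocol 3.1).

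Scan age at first dose = R + D - S. The SAP rejects an age above 28, that is, R - S > 28 - D.

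- D = 7: rejected when R - S is 22 or more.
- D = 0: rejected when R - S is 29 or more.
- S = 0, R = 28, D = 7: age 28 + 7 - 0 = 35 days, 7 beyond the limit. With the same R and D, scans on days 0 to 6 after consent are all rejected (ages 35 down to 29).
- S = 0, R = 35, D = 7: age 42 days.

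So the conflict exists, but only for patients scanned at least 22 days before randomisation.

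**2. The plan's own event count.** Protocol 10.2: HR 0.57, one-sided 0.10, 80% power, 1:1. Schoenfeld: events = (1.2816 + 0.8416)² / (0.25 × (ln 0.57)²) = 4.508 / 0.0790 = 57.1, rounded up to 58. Power at 58 events is 0.805. The figure reproduces, and the window does not change it.

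**3. Effect on timing.** Inputs from protocol 10.2: 80 patients, 16 months' accrual, medians 4 and 7 months. Assumptions: uniform accrual, exponential PFS, no dropout, all 80 analysable, and k patients censored at randomisation. The documents give no value for k.

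Expected events at month T = (80 - k)/2 × [p4(T) + p7(T)], where pm(T) = 1 - [exp(-λ(T - 16)) - exp(-λT)] / (16λ) and λ = ln 2 / m. At T = 20, p4 = 0.831 and p7 = 0.662, so k = 0 gives 40 × 1.493 = 59.7.

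| k of 80 | Events at month 20 | Month of 58th event | Delay (months) |
|---|---|---|---|
| 0 | 59.7 | 19.34 | – |
| 2 | 58.2 | 19.90 | 0.56 |
| 4 | 56.7 | 20.55 | 1.21 |
| 8 | 53.8 | 22.16 | 2.82 |

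A simulation (2,500 trials per row) that dates each event at the next 8-weekly scan puts the 58th event at month 20.19, 20.73, 21.31 and 22.87. The delays are 0.54, 1.12 and 2.68 months.

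**4. Effect on power.** In the same simulation, the stratified log-rank test at 58 counted events has power 0.776, 0.774, 0.781 and 0.764 for k = 0, 2, 4 and 8 (Monte Carlo SE 0.008; 20% bone-only and 50% US assumed). There is no material change.

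**5. Early deaths.** The SAP 3.1 bullet on inadequate baseline has no exception for death. Table 3.1 has an event row for early death with no condition on baseline. In the table as supplied, the inadequate-baseline entry runs into a second one that requires no "death prior to first scheduled assessment", and both share one date and outcome. Whether that condition covers both entries cannot be told from the text.

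**The case against.** **The SAP belongs to another trial.** It differs from this protocol in strata, allocation and event count as well, and protocol section 10 expects a SAP to be completed before database lock. This stands as a condition: the point applies only as far as this text is used or adapted. It does not remove the point, because a clause like this can survive an update that changes only the design, strata and event count.

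**Few patients may be affected.** HRG testing can be done under a separate biomarker consent (protocol synopsis and 7.2), so that step need not fall between main consent and randomisation. Protocol 7.7 also refers to image acquisition guidelines that were not supplied and might limit scan age. Both stand; the frequency is unknown and may be small.

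**Rejecting a stale baseline is legitimate.** It is, and the protocol has a similar censoring rule. But the two documents must then agree on what counts as stale.

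**Stronger readings that the documents do not support.** A reader might infer lost power; the analysis is triggered by 58 events, and power at 58 is unchanged. A reader might infer bias between arms; nothing shows it, and scan age is settled by the first dose in a double-blind trial. A reader might blame the window for overrunning 20 months; with scan-dated events the plan already averages 20.2 months with nobody affected. A reader might add standard-of-care scans taken before consent, citing protocol 11.2; that section covers source documents and only certain assessments, and 6.3 opens the window after consent, so the matter is unsettled. A reader might call the early-death rules a firm contradiction; that rests partly on a table whose layout was lost.

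**Conclusion.** The concern holds, conditional on this SAP being used or adapted for the present trial. Followed as written, its definition of an inadequate baseline would remove documented progressions of eligible, protocol-compliant patients from the primary PFS. The 35-day example rests on day arithmetic and on the absence, in the supplied text, of any cap from main consent to randomisation.

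The size is modest and cannot be fixed from the documents. If 2 of 80 patients were affected, the 58th event would come about 0.6 month later; if 4, about 1.2 months later. The main cost is the exclusion of those patients' events. Neither power loss nor bias is shown. It should be corrected before database lock because the rule is wrong as stated, not merely incomplete. How early deaths are handled when the baseline is inadequate is unclear and needs a sentence.

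**What to change.** First settle whether this SAP governs the trial. Then, when it is aligned to this protocol:

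1. State one baseline-scan window with one anchor in both documents. Define *valid* (protocol synopsis) and *inadequate* (SAP 4.2 and appendix) by it, so that an evaluable pre-dose scan that met the protocol is not classed as inadequate. Correct the impossible date condition in SAP 4.2.
2. Limit censoring at randomisation to patients with no usable baseline. Keep patients with an out-of-window but evaluable pre-dose scan in the primary PFS, and run their censoring as a sensitivity analysis. The documents do not require this choice; it is the one that keeps randomised patients' events.
3. Say whether the early-death event row of Table 3.1 also applies to patients with an inadequate baseline, and word the SAP 3.1 bullet to match.

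The cost is SAP wording and derivation code. If the protocol's anchor is moved instead, one footnote in 6.1 changes, and patients already scanned under the present footnote still need the rule in item 2. No new visits or data are needed.

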## 4.3 Safety Data

Missing adverse event, vital sign, ECG, or laboratory data will be considered missing in summary analyses.

#### 4.4 Pharmacokinetic Parameters

Missing values will be considered missing for summarizations and analyses. NC will be set to missing. In all data presentations other than listings, concentrations below the limit of quantification (BLQ) will be set to zero. The listings will report BLQ as < LLQ or lower limit of quantification.

Summary tables and plots will be calculated by setting missing concentrations if a concentration has been collected as ND (i.e., not done) or NS (i.e., no sample) or NC (i.e., not computable) or a deviation in sampling time is of sufficient concern or a concentration has been flagged as a data anomaly. Individual observations with known to bias the plasma concentration due to an unexpected event will be described and not included in summarizations or analysis.

## 4.5 Biomarkers

Missing or indeterminate HRG values considered as HRG positive will be not be included as part of the primary efficacy analysis. Patients with missing baseline biomarker assessments will not be used in analysis that will include baseline biomarker information. No missing data will be imputed.

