#### 3.9 Biomarkers

Baseline serum and tissue samples will be collected. Continuous and categorical type of biomarkers may be available. For continuous biomarkers, the value at and above the median will be used to determine the high group, while the low group is below. Categorical parameters will be classified into a maximum of three groups. Additional analyses will be considered exploratory in nature. Samples will be used to assess additional clinically relevant biomarkers, including but not limited to expression levels of the ErbB3 receptor, cMET, IGF-1R, and FGF receptor tyrosine kinases and will include assessment of their respective ligands (e.g. HGF, FGF-2, IGF-1, and IGF-2 mRNA or protein).

The only biomarker detailed in this SAP will be HRG positive as per the primary efficacy population analysis.

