## 5.3.2 Analysis of Key Time-to-Event Endpoints

Time-to-event endpoints between two treatment arms will be compared with a 1-sided,  $\alpha = 0.025$ , stratified logrank test, unless specified otherwise. Stratification factors will include: prior chemotherapy use (yes, no), chemotherapy backbone (exemestane or fulvestrant), and geographic region (US, Non-US/Non-Asia, Asia). Stratified Cox proportional hazards models will be constructed with stratification factors and treatment in the model to estimate hazard ratio and 2-sided 95% confidence interval (CI).

Additional comparisons between treatment groups will be performed using an unstratified log-rank test. Cox proportional hazards model with treatment group only will be constructed to estimate the hazard ratio and 2-sided 95% confidence intervals.

Potential influences of other baseline patient characteristics on various populations may be explored. Candidate covariates for the multivariate model will be selected using a stepwise selection process with treatment always in the model. Only covariates significant at a 15% level will be entered in the model and covariates significant at

15% will be considered for the final multivariate model. Treatment-by-covariate effects will be explored only for the set of factors included in the final model. The estimated hazard ratio and 2-sided 95% CI will be reported. Forest plots will be displayed for subgroup analyses.

The assumption of proportional hazards will be explored using a variety of graphical displays and testing. Hazard ratios and log (-log) of the survival probability estimates over time will be graphed. A scatterplot of smoothed Schoenfeld residuals over log of time will be displayed to check the primary efficacy analysis assumptions. The assumption of proportional hazards will be reviewed for the primary efficacy endpoint using the available graphical information. No formal testing will be performed in place of the stratified log-rank, if the assumption of proportional hazards does not hold.

Kaplan-Meier methods will be used in estimating the probability of event and displayed graphically. Time-toevent calculations will be performed in months unless specified otherwise. Median event times and 2-sided 95% CI will be provided based on Brookmeyer-Crowley methods. Probability of event estimates at 6, 9, 12, 15, and 18 month intervals will be reported in tables.

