## 5.4.4 Prior Systemic Cancer Treatment

The following will be summarized categorically unless stated as a continuous parameter.

- Type of prior anti-cancer treatment
- Number of prior anti-cancer treatment
- Time since last anti-cancer treatment prior to study enrollment will be summarized as a continuous parameter

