## 5.5.2 PFS Sensitivity and Subgroup Analysis

PFS will be performed using a variety of methodology to assess the sensitivity to deviations and covariate factors. The same one-sided significance level at 0.025 will be used for all situations.

- Unstratified log-rank test will be performed and a Cox proportional hazards model with treatment only in the model to estimate the hazard ratio and 95% confidence intervals
- Treatment group comparison using interval-censored methods
- Evaluation of influences of baseline covariates and biomarker factors using stepwise selection methods
- Treat all censors on the seribantumab arm as events on the date of censorship
- Cox proportional hazard models will include treatment and covariate in the model. Additional models will include treatment, covariate, and the interaction effect in the model. Hazard ratios and 95% confidence intervals will be reported for all models. In addition, median event estimates and 95% confidence intervals will be reported. Forest plots of the hazard ratio estimates and confidence intervals will be displayed for the aforementioned models.

PFS will also be analyzed using IRR. PFS will be analyzed using a stratified Cox proportional hazard models similar to the primary analysis. Cox proportional hazard models will include treatment and covariate in the

model. Additional models will include treatment, covariate, and the interaction effect in the model. Hazard ratios and 95% confidence intervals will be reported for all models. In addition, median event estimates and 95% confidence intervals will be reported. Forest plots of the hazard ratio estimates and confidence intervals will be displayed with for the aforementioned models.

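### The stepwise PFS sensitivity analysis, read with the SAP's missing-biomarker rule, would estimate its treatment hazard ratio only in biomarker-complete patients

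*SAP*

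**What the plan says.** Three SAP rules meet here.

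- **SAP 5.5.2**, among the PFS sensitivity analyses: "Evaluation of influences of baseline covariates and biomarker factors using stepwise selection methods".
- **SAP 5.3.2**, on how the search runs: "Candidate covariates for the multivariate model will be selected using a stepwise selection process with treatment always in the model". Entry and retention are both at the 15% level, and the hazard ratio is reported with a two-sided 95% CI.
- **SAP 4.5**, on missing markers: "Patients with missing baseline biomarker assessments will not be used in analysis that will include baseline biomarker information". It adds: "No missing data will be imputed".

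Other planned analyses bear on the point. SAP 5.5.2 also says: "Cox proportional hazard models will include treatment and covariate in the model", with further models adding an interaction. SAP 5.5.4 relates each biomarker, in groups, to PFS and OS.

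On sources, SAP 3.9 says: "Baseline serum and tissue samples will be collected". It gives an open-ended list of receptors and ligands, then limits itself: "The only biomarker detailed in this SAP will be HRG positive as per the primary efficacy population analysis".

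The covariates named in SAP 3.8 include no biomarker, but the list is left open for additions. ECOG status and visceral metastasis (SAP 5.4.2) and "Number of prior anti-cancer treatment" (SAP 5.4.4) are summarised at baseline but are not named in 3.8.

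**The concern.** A covariate-adjusted sensitivity analysis should show whether the primary treatment effect holds up when prognostic imbalance is taken into account. That comparison is clean only if both estimates use the same patients.

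A stepwise search compares models holding different candidates. It is ordinarily run on patients with every candidate observed, so a patient lacking one candidate marker leaves the search, and the treatment estimate with it, even if that marker is never selected. The SAP does not call for a refit on all patients, nor for an unadjusted hazard ratio in the reduced set. If the adjusted and primary hazard ratios then differed, a reader could not tell adjustment from patient loss.

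The other planned models do not fill the gap. The remaining Cox models in SAP 5.5.2 are worded as treatment plus one covariate, and the analyses in SAP 5.5.4 are about markers. On that reading no planned analysis is a multi-covariate check on all patients.

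**Working it through.** **Inputs.** From protocol 10.2: 58 PFS events, 1:1 allocation, HR 0.57 (medians 4 v 7 months), one-sided alpha 0.10, 80% power. From SAP 5.5.2: one-sided 0.025 for every PFS sensitivity analysis. From SAP 5.1: about 195 events, 2:1, one-sided 0.025, at least 95% power. Neither document gives a missing-marker rate.

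**Step 1: reproduce the stated figures (Schoenfeld).**

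- Protocol: events = 4 × (1.2816 + 0.8416)² / (ln 0.57)² = 4 × 4.508 / 0.316 = 57.1, rounded up to 58. Power with 58 events = Φ(√(58/4) × 0.562 − 1.2816) = 80.5%.
- SAP: power with 195 events at 2:1 = Φ(√(195 × 2/9) × 0.562 − 1.96) = 95.9%.

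Both agree with the documents.

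**Step 2: what patient loss would do.** Assume a fraction m of patients lack at least one candidate marker and that events fall in proportion, so D = 58 × (1 − m). Power = Φ(√(D/4) × 0.562 − z). The approximate 95% CI around 0.57 is 0.57 × exp(±1.96 × 2/√D).

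| Assumed m | Events D | Power, one-sided 0.10 | Power, one-sided 0.025 | 95% CI at HR 0.57 |
|---|---|---|---|---|
| 0% | 58 | 80.5% | 57% | 0.34–0.95 |
| 10% | 52 | 77% | 53% | 0.33–0.98 |
| 20% | 46 | 74% | 48% | 0.32–1.01 |
| 30% | 41 | 70% | 43% | 0.31–1.05 |
| 40% | 35 | 65% | 38% | 0.29–1.11 |
| 50% | 29 | 59% | 33% | 0.28–1.18 |

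**Step 3: several markers.** Three markers, each missing independently in 10%, leave 0.9³ = 72.9% of patients, or about 42 events. If the same 10% lack all three, 90% remain, or about 52 events.

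**Step 4: at the SAP's own event count.** At 195 events and 2:1, a loss of 10% leaves 175.5 events (power 93.9%) and a loss of 50% leaves 97.5 (74.4%). More events soften the loss of power but do not make the two hazard ratios comparable.

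**Step 5: is missingness foreseeable?** Protocol 3.1 asks patients tested on archived tissue for a fresh research biopsy. Protocol 8.7.1 seeks a second core or aspirate only where possible, and 8.7.5 collects archived samples only if they exist. Some missing tissue markers are therefore plausible, but no rate can be derived.

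**The case against.** The strongest reply is that the SAP never states there is one joint model. The 5.5.2 bullet refers to methods in the plural, 5.3.2 speaks of patient characteristics and says they may be explored, 3.8 names no biomarker, and 3.9 details only HRG. This stands as far as it goes: the single model is a reading. It is still the natural one. The bullet puts covariates and biomarkers under one procedure, and HRG positivity is constant in the SAP's primary efficacy population (SAP 2.1), so the biomarker factors must be something else, such as HRG score level or other markers.

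A reader might infer three stronger things that the documents do not support.

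- **That the analysis rests on a tissue-selected group.** Serum is collected from all patients (protocol 8.7.3), and every randomized patient needs a central HRG result. The protocol's per-protocol primary set already requires HRG confirmation on fresh tissue (protocol 10.3), so within that set refusal of the biopsy cannot explain a difference between the two hazard ratios. Insufficient material or assay failure could. The supportable term is biomarker-complete.
- **That most events would be lost.** Counting the eight markers named in SAP 3.9 and assuming each is missing independently in 10% gives 0.9⁸ = 43%, or about 25 events. But that list is open-ended and is not a declared candidate set, and markers from one sample tend to be missing together. Full overlap at 10% leaves 52 events and a barely wider interval.
- **That no other covariate-adjusted PFS analysis exists.** The treatment-plus-covariate models in SAP 5.5.2 lose nobody for missing markers unless the covariate is itself a marker.

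It is also fair to say that SAP 5.5.4 already plans marker-by-PFS analyses showing event counts, which is part of the remedy.

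**Conclusion.** The point holds as a minor one. Read together, SAP 5.5.2, 5.3.2 and 4.5 would estimate the stepwise treatment hazard ratio in biomarker-complete patients only, with no stated way to separate adjustment from patient loss. This rests on the joint-search reading and on no refit to all patients.

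The size is conditional. An assumed 10% to 50% missing, with events lost in proportion, takes 58 events to between 52 and 29 and power at one-sided 0.025 from 57% to between 53% and 33%. With complete markers the effect is nil.

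It would be wrong to infer that the primary result is at risk. The stratified log-rank test uses no marker beyond HRG status, and the plan ties no decision to the stepwise analysis.

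Applying this SAP to 58 events also assumes that it governs this trial. It is written for protocol seribantumab-02-03-10, with 195 events, 2:1 allocation and one-sided 0.025. This protocol is MM-121-02-02-10, with 58 events, 1:1 and one-sided 0.10. That mismatch is the larger matter and must also be reconciled.

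**What to change.** 1. In SAP 5.5.2, replace the joint stepwise search with one Cox model for PFS on the full primary set, stratified as randomized (bone-only disease and US v non-US under protocol 5.1). Adjust for a short fixed list of factors already recorded, for example ECOG 0 v 1, visceral disease and number of prior lines. Use no selection step and no biomarkers. SAP 3.8 leaves room for these factors but does not commit to them.
2. Keep biomarkers in separate exploratory models alongside SAP 5.5.4. For each, report N, events, and the treatment hazard ratio without the marker in the same subset.
3. Limit the exclusion rule in SAP 4.5 to the models in item 2.
4. Reconcile the SAP with this protocol on protocol number, events, allocation, alpha, stratification factors and primary population, so that the full primary set has one meaning.

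Items 1 to 3 cost some SAP wording and simple programming, with no new data. The downside is that no single model holds all markers at once. The covariate model keeps up to 58 events, provided the chosen factors are complete.
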